9.2.5 Events of Clinical Interest (pembrolizumab)

Selected non-serious and serious adverse events are also known as Events of Clinical Interest (ECI) and must be reported within 2 working days to Merck Global Safety. (Attn: Worldwide Product Safety; [contact]).

For the time period beginning when the consent form is signed until treatment allocation/randomization, any ECI, or follow up to an ECI, that occurs to any participant must be reported within 2 working days to Merck Global Safety if it causes the participant to be excluded from the trial, or is the result of a protocol-specified intervention, including but not limited to washout or discontinuation of usual therapy, diet, placebo treatment or a procedure.

For the time period beginning at treatment allocation through 90 days following cessation of treatment, or 30 days following cessation of treatment if the participant initiates new anticancer therapy, whichever is earlier, any ECI, or follow up to an ECI, whether or not related to Merck product, must be reported within 2 working days to Merck Global Safety.

Events of clinical interest for this trial include:

1. an overdose of Merck product, as defined in section 9.2.4 - Definition of an Overdose for This Protocol and Reporting of Overdose to the Sponsor, that is not associated with clinical symptoms or abnormal laboratory results.
2. an elevated AST or ALT lab value that is greater than or equal to 3X the upper limit of normal and an elevated total bilirubin lab value that is greater than or equal to 2X the upper limit of normal and, at the same time, an alkaline phosphatase lab value that is less than 2X the upper limit of normal, as determined by way of protocol-specified laboratory testing or unscheduled laboratory testing.*

*Note: These criteria are based upon available regulatory guidance documents. The purpose of the criteria is to specify a threshold of abnormal hepatic tests that may require an additional evaluation for an underlying etiology.

9.2.6 Recording AEs/SAEs in the Case Report Form

AEs can be assessed directly by the Investigator during a clinical visit or based on laboratory/Instrumental examinations or can be referred by the patient.

Pre-existing Conditions

A pre-existing condition (i.e., a disorder starting before the adverse event reporting period) should not be reported as an adverse event unless the condition worsens during the adverse event reporting period.

Procedures

Diagnostic and therapeutic procedures, such as surgery, should not be reported as adverse events, while the medical condition for which the procedure was performed should be reported if it meets the definition of an adverse event. For example, an appendectomy performed for an acute appendicitis occurring during the adverse event reporting period should not be reported as adverse event; while “acute appendicitis” is to be reported as adverse event. If a patient undergoes a surgical procedure that was planned prior to entry into the trial, and surgery is not performed due to a worsening of a baseline condition, this baseline condition should not be reported as an adverse event.

Symptoms of Targeted Disease

Tumor-related signs and symptoms will be followed at each visit. Although a measure of efficacy, these will always be reported as pre-existing conditions at baseline and during treatment only if they meet the definition of adverse event.

For all adverse events the Investigator will be asked to assess its relationship with the study treatment.

Causality Assessment and Grading of Adverse Event Severity

The assessment of relationship to study drug will be done according to the following causality scale based on the WHO definitions:

- Certain: A clinical event, including laboratory test abnormality, occurring in a plausible time relationship to drug administration, and which cannot be explained by concurrent disease or other drugs or chemicals. The response to withdrawal of the drug (de-challenge) should be clinically plausible. The event must be definitive pharmacologically or phenomenologically, using a satisfactory re-challenge procedure if necessary
- Probable: A clinical event, including laboratory test abnormality, with a reasonable time sequence to administration of the drug, unlikely to be attributed to concurrent disease or other drugs or chemicals, and which follows a clinically reasonable response on withdrawal (rechallenge). Rechallenge information is not required to fulfil this definition.

- Possible: A clinical event, laboratory test abnormality, with a reasonable time sequence to administration of the drug, but which could also be explained by concurrent disease or other drugs or chemicals. Information on drug withdrawal may be lacking or unclear
- Unlikely: A clinical event, laboratory test abnormality, with a temporal relationship to drug administration which makes a causal relationship improbable, and in which other drugs, chemicals or underlying disease provide plausible explanations Severity grading of adverse events and pre-existing conditions will be done according to the National Cancer Institute (NCI) Common Toxicity Criteria (CTCAE) V. 4.03.

AEs that are not defined in the NCI CTCAE should be evaluated for severity according to the following scale:

- Grade 1 = Mild – transient or mild discomfort; no limitation in activity; no medical intervention/therapy required;
- Grade 2 = Moderate – mild to moderate limitation in activity, some assistance may be needed; no or minimal medical intervention/therapy required;
- Grade 3 = Severe – marked limitation in activity, some assistance usually required; medical intervention/therapy required, hospitalization is possible;
- Grade 4 = Life threatening – extreme limitation in activity, significant assistance required; significant medical intervention/therapy required, hospitalization or hospice care probable;
- Grade 5 = Death - the event results in death.

Note the distinction between the gravity and the severity of an adverse event. Severe is a measure of intensity; thus, a severe reaction is not necessarily a serious reaction. For example, a headache may be severe in intensity but would not be classified as serious unless it meets one of the criteria for serious events listed above.

Pregnancy Reporting

Although pregnancy and infant exposure during breast feeding are not considered adverse events, it is the responsibility of investigators or their designees to report any pregnancy or lactation in a participant (spontaneously reported to them) that occurs during the study using the “exposure in utero” form.

Pregnancies and infant exposures during breastfeeding that occur after the consent form is signed but before treatment allocation/randomization must be reported by the investigator if they cause the participant to be excluded from the trial, or are the result of a protocol-specified intervention, including but not limited to washout or discontinuation of usual therapy, diet, placebo treatment or a procedure.

Pregnancies and infant exposures during breastfeeding that occur from the time of treatment allocation/randomization through 120 days (pembrolizumab) or 90 days (temozolomide) following cessation of study product, or 30 days following cessation of treatment if the participant initiates new anticancer therapy, whichever is earlier, must be reported by the investigator to delegated Pharmacovigilance within 2 weeks of learning of its occurrence.. All reported pregnancies must be followed to the completion/termination of the pregnancy. Pregnancy outcomes of spontaneous abortion, missed abortion, benign hydatidiform mole, blighted ovum, fetal death, intrauterine death, miscarriage and stillbirth must be reported as serious events (Important Medical Events). If the pregnancy continues to term, the outcome (health of infant) must also be reported.

Such events must be reported within 24 hours to delegated Pharmacovigilance and within 2 working days hours to Merck Global Safety. (Attn: Worldwide Product Safety; [contact]).

Overdose

Reporting if any overdose (accidental or intentional) which results in serious adverse reactions is to be handled following the SAE procedures. This includes reports related to drug intake with suicidal intentions and consequent drug overdose.

Overdose reporting even not associated with adverse reactions shall be anyhow reported immediately to delegated Pharmacovigilance using the most rapid type of communication (phone, e-mail).

Follow-up of Unresolved Adverse Events

All adverse events should be followed at least until 30 days following the last dose of IMP. Drug-related and serious adverse events ongoing at the end of this observation period must be recorded until they are resolved or the investigator assesses them as chronic or the subject is lost to follow-up or starts a new anti-cancer treatment, whichever occurs earlier.

Table 9.2 Evaluating Adverse Events

An investigator who is a qualified physician, will evaluate all adverse events as to:

V4.03 CTCAE Grading	Grade 1	Mild; asymptomatic or mild symptoms; clinical or diagnostic observations only; intervention not indicated.
	Grade 2	Moderate; minimal, local or noninvasive intervention indicated; limiting age-appropriate instrumental ADL.
	Grade 3	Severe or medically significant but not immediately life-threatening; hospitalization or prolongation of hospitalization indicated; disabling; limiting self-care ADL.
	Grade 4	Life threatening consequences; urgent intervention indicated.
	Grade 5	Death related to AE
Seriousness	A serious adverse event is any adverse event occurring at any dose or during any use of Merck product that:	
	† Results in death ; or	
	† Is life threatening ; or places the participant, in the view of the investigator, at immediate risk of death from the event as it occurred (Note: This does not include an adverse event that, had it occurred in a more severe form, might have caused death.); or	
	† Results in a persistent or significant disability/incapacity (substantial disruption of one’s ability to conduct normal life functions); or	
	† Results in or prolongs an existing inpatient hospitalization (hospitalization is defined as an inpatient admission, regardless of length of stay, even if the hospitalization is a precautionary measure for continued observation. (Note: Hospitalization for an elective procedure to treat a pre-existing condition that has not worsened is not a serious adverse event. A pre-existing condition is a clinical condition that is diagnosed prior to the use of a Merck product and is documented in the patient’s medical history.); or	
	† Is a congenital anomaly/birth defect (in offspring of participant taking the product regardless of time to diagnosis);or	
	Is a new cancer (that is not a condition of the study) (although not serious per ICH definition, is reportable to the Sponsor within 24 hours and to Merck within 2 working days to meet certain local requirements); or	
	Is an overdose (whether accidental or intentional). Any adverse event associated with an overdose is considered a serious adverse event for collection purposes. An overdose that is not associated with an adverse event is considered a non-serious event of clinical interest and must be reported within 24 hours to the Sponsor and to Merck within 2 working days..	
Other important medical events that may not result in death, not be life threatening, or not require hospitalization may be considered a serious adverse event when, based upon appropriate medical judgment, the event may jeopardize the participant and may require medical or surgical intervention to prevent one of the outcomes listed previously (designated above by a †).		
Duration	Record the start and stop dates of the adverse event. If less than 1 day, indicate the appropriate length of time and units	
Action taken	Did the adverse event cause Merck product to be discontinued?	
Relationship to Merck Product	Did Merck product cause the adverse event? The determination of the likelihood that Merck product caused the adverse event will be provided by an investigator who is a qualified physician. The investigator’s signed/dated initials on the source document or worksheet that supports the causality noted on the AE form, ensures that a medically qualified assessment of causality was done. This initialed document must be retained for the required regulatory time frame. The criteria below are intended as reference guidelines to assist the investigator in assessing the likelihood of a relationship between the test drug and the adverse event based upon the available information.	
	The following components are to be used to assess the relationship between Merck product and the AE ; the greater the correlation with the components and their respective elements (in number and/or intensity), the more likely Merck product caused the adverse event (AE):	
	Exposure	Is there evidence that the participant was actually exposed to Merck product such as: reliable history, acceptable compliance assessment (pill count, diary, etc.), expected pharmacologic effect, or measurement of drug/metabolite in bodily specimen?
	Time Course	Did the AE follow in a reasonable temporal sequence from administration of Merck product? Is the time of onset of the AE compatible with a drug-induced effect (applies to trials with investigational medicinal product)?
	Likely Cause	Is the AE not reasonably explained by another etiology such as underlying disease, other drug(s)/vaccine(s), or other host or environmental factors

Relationship to Merck Product (continued)	The following components are to be used to assess the relationship between the test drug and the AE: (continued)	
	Dechallenge	Was Merck product discontinued or dose/exposure/frequency reduced? If yes, did the AE resolve or improve? If yes, this is a positive dechallenge. If no, this is a negative dechallenge. (Note: This criterion is not applicable if: (1) the AE resulted in death or permanent disability; (2) the AE resolved/improved despite continuation of the Sponsor's product; or (3) the trial is a single-dose drug trial); or (4) Sponsor's product(s) is/are only used one time.)
	Rechallenge	Was the participant re-exposed to Merck product in this study? If yes, did the AE recur or worsen? If yes, this is a positive rechallenge. If no, this is a negative rechallenge. (Note: This criterion is not applicable if: (1) the initial AE resulted in death or permanent disability, or (2) the trial is a single-dose drug trial); or (3) Sponsor's product(s) is/are used only one time. NOTE: IF A RECHALLENGE IS PLANNED FOR AN ADVERSE EVENT WHICH WAS SERIOUS AND WHICH MAY HAVE BEEN CAUSED BY MERCK PRODUCT, OR IF REEXPOSURE TO MERCK PRODUCT POSES ADDITIONAL POTENTIAL SIGNIFICANT RISK TO THE PARTICIPANT, THEN THE RECHALLENGE MUST BE APPROVED IN ADVANCE BY THE SPONSOR AS PER DOSE MODIFICATION GUIDELINES IN THE PROTOCOL.
	Consistency with Trial Treatment Profile	Is the clinical/pathological presentation of the AE consistent with previous knowledge regarding Merck product or drug class pharmacology or toxicology?
The assessment of relationship will be reported on the case report forms /worksheets by an investigator who is a qualified physician according to his/her best clinical judgment, including consideration of the above elements.		
Record one of the following	Use the following scale of criteria as guidance (not all criteria must be present to be indicative of Merck product relationship).	
Yes, there is a reasonable possibility of Merck product relationship.	There is evidence of exposure to Merck product. The temporal sequence of the AE onset relative to the administration of Merck product is reasonable. The AE is more likely explained by Merck product than by another cause.	
No, there is not a reasonable possibility of Merck product relationship	Participant did not receive the Merck product OR temporal sequence of the AE onset relative to administration of Merck product is not reasonable OR the AE is more likely explained by another cause than the Merck product. (Also entered for a participant with overdose without an associated AE.)	

9.2.7 Sponsor Responsibility for Reporting Adverse Events

All Adverse Events will be reported to regulatory authorities, IRB/IECs and investigators in accordance with all applicable global laws and regulations.

10.0 STATISTICAL CONSIDERATIONS

10.1 General considerations

The hypothesis tested by ARETHUSA is whether immunoediting in MMR proficient cancers can be disrupted by increasing the tumor mutational load with TMZ, enabling the tumor to dynamically express neo-antigens that positively affect T cell functions under check-point inhibition.

The main analysis thus will concern the response to pembrolizumab in MMR proficient patients (cohort P) with measurable disease at baseline who have received at least 1 cycle of pembrolizumab (iEE population, see 10.3.1).

10.2 Sample size calculation

A two-stage Green-Dahlberg design has been used [Green SJ and Dahlberg S Statistics in Medicine 11:853-862,1992], to calculate the sample size for the **P-cohort** under the following assumptions:

- The null hypothesis that the true (H_0) response rate is 10% (not considered clinically compelling) will be tested against a one-sided alternative (H_1).
- In the first stage, 10 patients will be accrued. If no responses are observed, the study will be stopped. Otherwise, 10 additional patients will be accrued for a total of 20.
- The null hypothesis will be rejected if 5 or more responses are observed in 20 patients.
- This design yields a type I error rate of .05, and power of 90% when the true response rate is 40%.
- In order to recruit 20 patients in the P-cohort the number of MMR unselected patients to be pre-screened for MMR status MGMT promoter methylation and the number of MGMT-PM+ to be primed with TMZ are reported in Table 10.1. below as well as in Study Diagram, section 4.2.

Table 10.1 Number of patients required in each trial Phase.

Number of Patients to be:	N	Expected Percent
RAS mut MMR proficient cases to be screened	670	A
expected MGMT IHC negative	335	B = 50% of A
expected promoter methylated in tissue	67	C=20% of B and 10% of A
expected with increase of mutational load ≥ 20 mutations/Mb (PRIMING Phase)	20	D= 30% of C

For cohort D, a precise sample size has NOT been calculated since the ORR in deficient patients is a secondary objective of the trial. We will enroll up to 34 MMR-D cases according to an estimated prevalence of 4-5 %. These patients will constitute the **D-cohort**. We expect a response rate between 40% (95% C.I. .18-.71) and 33% (95% C.I. .21-.46) as reported by Le et al., (2015 & 2019) with 11-14 responses accordingly.

10.3 Statistical Analysis Plan

10.3.1 Populations considered for the analysis

All patients signing the informed consent for the PRIMING and TRIAL Phases will be accounted for. The number of patients who will not result eligible, who died or withdrew before these phases, will be specified.

A patient will be considered to be PRIMING and TRIAL Phases eligible if he/she did not have any deviation from the patient entry criteria listed in section 7.1.2 (PRIMING) and 7.1.3 (TRIAL). Potential eligibility problems will be assessed by the Clinical Study Coordinator at time of medical review.

The final efficacy analysis will occur after 20 patients entered in the P-Cohort are evaluable for response according to RECIST 1.1. The distribution of follow-up time in both cohorts (P and D) will be described and the number of patients lost to follow-up will be reported.

Conclusions will be based on all eligible patients in each cohort. Further analysis may be performed excluding those patients for whom major protocol deviations have been identified (e.g., early death due to other reasons, early discontinuation of treatment, major protocol violations, etc.). However, these sub-analyses may not serve as the basis for drawing conclusions concerning treatment efficacy, and the reasons for excluding patients from the analysis should be clearly reported.

Three populations will be considered for the analysis, as follows:

- The Safety Evaluable (SE) population defined as all treated patients (i.e. eligible as decided at the time of registration that receives at least 1 dose of any study treatment i.e. TMZ and Pembrolizumab). An incorrect treatment schedule or drug administration or an early termination of treatment does not result in exclusion of patients from this population. This population will be the object of the Safety and Tolerability analysis. Patients with major deviations from the eligibility criteria affecting safety or from the treatment schedule at cycle 1 for reasons other than toxicity may be presented in separate tables/listings.
- The Efficacy Evaluable (EE) population defined as all patient treated with pembrolizumab in P-cohort, with no major deviations from the eligibility criteria affecting efficacy evaluation, for which the tumor response could be evaluated at least once while on treatment. These patients should have received at least 2 cycles after treatment starts, unless disease progression occurs within this period.
- The immunotherapy Efficacy Evaluable (iEE) population. Anti-tumor immune responses such as those associated with pembrolizumab may result in objective responses that are delayed and that can be preceded by initial apparent radiological progression. This initial apparent progression may occur as a result of either delayed anti-tumor activity and/or robust tumor immune cell infiltration with a concomitant increase in tumor size. In addition, lesions that might otherwise be undetectable with conventional imaging may increase in size as a result of these processes and be recorded as new lesions. Conventional RECIST 1.1 response criteria may not be thus adequate to capture and describe the anti-tumor activity of pembrolizumab. Therefore, modified response criteria have been developed that account for the possible appearance of new lesions and allow radiological progression to be confirmed at subsequent assessment. For these reason a second efficacy analysis will be conducted (iEE analysis) on the same population used for the EE analysis using the Modified RECIST criteria.

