10.3.2 Primary analysis

The main analysis will focus on the objective response rate (ORR) of the P Cohort.

An objective response is defined as either a CR or PR assessed, as outlined in sections 9.1.3 and 10.3.1 (iEE population), first by RECIST 1.1 and then by iRECIST criteria at the discretion of the local Investigator.

Best objective response of either type will be centrally confirmed using the [Quibim Precision[®]](#) software (the cloud-based repository for radioimaging). In case of disagreement between local and central evaluation, the central response evaluation will be used for the analysis. The duration of response will be calculated accordingly.

An estimate of ORR and its 95% CIs will be calculated using the Clopper-Pearson method. Discrepant results, impinging in the acceptance of rejection of the null hypothesis, will be discussed and agreed upon between the Protocol Chair and the Sponsor.

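### The patient set for the primary ORR is defined in contradictory ways, and the EE/iEE definition would drop treated patients who were never evaluated instead of counting them as non-responders

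*Combined protocol and SAP*

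**What the plan says.** Several statements bear on the primary denominator.

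- Section 10.1 places the main analysis in cohort P patients "with measurable disease at baseline who have received at least 1 cycle of pembrolizumab (iEE population, see 10.3.1"). No on-treatment assessment is required.
- Section 10.3.1 defines EE as pembrolizumab-treated cohort P patients without major eligibility deviations affecting efficacy, "for which the tumor response could be evaluated at least once while on treatment". It adds: "These patients should have received at least 2 cycles after treatment starts, unless disease progression occurs within this period".
- Section 10.3.1 then defines iEE by reference to EE: "a second efficacy analysis will be conducted (iEE analysis) on the same population used for the EE analysis using the Modified RECIST criteria".
- Section 10.3.2 opens with "The main analysis will focus on the objective response rate (ORR) of the P Cohort" and, in defining a response, cites 10.3.1 and the iEE population.
- Section 10.3.1 also states: "Conclusions will be based on all eligible patients in each cohort". Eligibility there means no deviation from the entry criteria of 7.1.2 and 7.1.3. The same paragraph allows further analyses that exclude, for example, early deaths from other reasons or early discontinuations, but bars them as a basis for efficacy conclusions.
- On the count of 20, section 10.2 says "Otherwise, 10 additional patients will be accrued for a total of 20", whereas 10.3.1 says "The final efficacy analysis will occur after 20 patients entered in the P-Cohort are evaluable for response according to RECIST 1.1".

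The protocol text does not say how a treated patient without a response assessment is counted. Section 7.8.2 replaces only patients who cannot complete the first infusion because of a severe infusion reaction.

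**The concern.** One label, iEE, has two incompatible definitions. A patient who receives one cycle and dies before any scan is inside the set described in 10.1 and outside the set described in 10.3.1. Section 10.3.2 points to 10.3.1.

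A patient who is never evaluated cannot be a documented responder. Removing such patients shrinks the denominator and leaves the numerator alone, so the ORR and both Clopper-Pearson limits move up whenever there is at least one response.

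Early loss is plausible here. Cohort P has failed standard therapy and progressed on temozolomide, may wait up to five weeks before pembrolizumab (4.1.2), and is then imaged every nine weeks (9.1.3.1). Imaging at discontinuation (9.1.3.1) recovers some of these patients, but not those who die first.

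What is at stake is mainly the estimate. Section 6.2.3.1 chose ORR for a historical comparison, and 10.3.2 reports it with a 95% interval, so the estimate is used as well as the pass/fail count.

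**Working it through.** **Inputs.** From 10.2: null rate 10%, one-sided; stop if 0 responses in the first 10; otherwise continue to 20 and reject with 5 or more; stated type I error 0.05 and power 90% at a 40% rate. From 10.3.2: Clopper-Pearson 95% interval. The documents give no non-evaluable share, so the values below are assumptions. Never-evaluated patients are taken as non-responders.

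**Step 1: the plan's own figures.** Let R(p) be the chance of rejecting at true rate p:

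R(p) = sum over x = 1..10 of Bin(x; 10, p) × P(Y ≥ 5 − x), with Y ~ Bin(10, p).

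Equivalently, take the single-stage tail for 20 patients and subtract the paths that start with 0 of 10:

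- R(0.10) = 0.0432 − 0.9^10 × P(Y ≥ 5) = 0.0432 − 0.3487 × 0.0016 = 0.0426.
- R(0.40) = 0.9490 − 0.6^10 × P(Y ≥ 5) = 0.9490 − 0.0060 × 0.3669 = 0.9468.

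The stated 0.05 and 90% are not the exact values, but they hold as bounds. The design arithmetic is not the problem.

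**Step 2: the estimate if 20 are accrued and k are dropped.** The ORR is multiplied by 20/(20 − k), which is 1.05, 1.11 and 1.18 for k = 1, 2 and 3. With 5 responses:

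| Dropped | ORR | 95% CI |
|---|---|---|
| 0 | 5/20 = 25.0% | 8.7-49.1 |
| 1 | 5/19 = 26.3% | 9.1-51.2 |
| 2 | 5/18 = 27.8% | 9.7-53.5 |
| 3 | 5/17 = 29.4% | 10.3-56.0 |

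With three dropped, the lower limit moves from below 10% to above it on the same five responders. With 8 responses, 8/20 = 40.0% becomes 8/17 = 47.1%.

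**Step 3: the decision if 20 are accrued.** The rule counts responders. Never-evaluated patients add none whether they are kept or dropped, so 5 of 20 and the type I error of 0.0426 do not change.

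**Step 4: the decision if enrolment runs to 20 evaluable patients.** Suppose also that the 10% null refers to all treated patients. With a non-evaluable share f, the null rate among evaluable patients becomes 0.10/(1 − f), and the type I error is R(0.10/(1 − f)):

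| f | Null rate among evaluable | Type I error |
|---|---|---|
| 5% | 10.5% | 0.051 |
| 10% | 11.1% | 0.062 |
| 15% | 11.8% | 0.076 |
| 20% | 12.5% | 0.094 |

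If either condition fails, it stays at 0.0426.

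**Step 5: power once everyone is counted.** If 40% holds only among evaluable patients, the all-treated rate is 0.40(1 − f). R(0.40(1 − f)) is then 0.925, 0.896, 0.859 and 0.813 at f = 5%, 10%, 15% and 20%. It crosses 90% at f of about 9.3%.

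**The case against.** The strongest reply is that the plan already has a governing rule. Section 10.3.1 bases conclusions on all eligible patients, defines eligibility by entry criteria and not by evaluability, and bars efficacy conclusions from analyses that leave out, for example, early deaths from other reasons or early discontinuations. That covers much of the scenario above. A reader might infer that the sponsor is free to choose the denominator after seeing the data; given this bar, the documents do not support so strong a reading. What remains is that 10.1 and 10.3.2 attach the primary analysis to iEE, whose definition in 10.3.1 conflicts with that rule, and that non-response for a missing assessment is never written down.

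A second reply is that the size is hypothetical. That is correct: no non-evaluable rate is documented, and the effect may be zero. A reader might also infer that the trial's type I error is inflated. That needs both conditions in step 4, and the documents establish neither. The planned 54 in the TRIAL Phase equals 20 + 34, which fits 20 accrued, but it would read the same for 20 evaluable with no allowance for attrition, so it does not settle the matter.

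Third, the documents do not give the historical study's denominator, so it cannot be said which set makes the comparison closer to like-for-like. This point does not rest on that. Finally, RECIST 1.1 is adopted by reference; the absence of a missing-response rule is checked only in the protocol text.

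**Conclusion.** The contradiction is certain, because it is in the text: two definitions of iEE, with the primary analysis tied to that label against the plan's own basis for conclusions. Following the EE/iEE definition biases the primary ORR and its interval upward whenever some treated patients are never evaluated and at least one patient responds. The size depends on an assumed count: one to three of 20 dropped multiplies the ORR by 1.05 to 1.18.

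The go/no-go decision is not shown to be affected. With 20 accrued it is unchanged, and a type I error of 0.051 to 0.094 arises only under the two conditions in step 4 with 5% to 20% non-evaluable. This should be fixed, but it does not invalidate the design.

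**What to change.** - In 10.1, 10.3.1 and 10.3.2, apply the existing all-eligible rule to the primary ORR: all eligible cohort P patients with measurable disease at baseline who started pembrolizumab, with a missing or non-evaluable response counted as non-response. Judge eligibility on the entry criteria, without reference to response.
- State that the 10 and the 20 in the two-stage rule count these patients, and reconcile the evaluable-patient trigger in 10.3.1 with this.
- Leave the planned response criteria (RECIST 1.1 and iRECIST) as they are; only the patient set changes. The evaluable-only EE/iEE set becomes supportive, with one cycle requirement in place of two.
- State that patients replaced under 7.8.2 fall outside the 20 used for the decision rule, and report the ORR also with them counted as non-responders.
- Use the same counting rule for cohort D.

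The cost is wording only, with no extra patients. The downside is a somewhat lower reported ORR and, if 40% holds only among evaluable patients, power below the stated 90% once about 9.3% are non-evaluable.
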